6.2.2 Adjudication

We will adjudicate potential AMI events identified from any diagnosis position using successfully implemented methods from previous studies: Cardiovascular Research Network (CVRN)^[26], Coronary Artery Risk Development in Young Adults (CARDIA)^[27], Cardiovascular Health Study (CHS)^[28], Atherosclerosis Risk in Communities (ARIC)^[29], and Women's Health Initiative^[30]. Abstracted information will be adjudicated independently by 2 trained cardiologist reviewers masked to vaccine exposure. Cases with disagreement will be reviewed by a third cardiologist. Adjudication will follow standardized criteria based on changes in troponin or other cardiac biomarker levels, cardiac signs and symptoms, clinical readings of the 12-lead ECGs, and imaging evidence, as outlined by the Third Universal Definition of Myocardial Infarction^[31]. All eligible hospitalized events will be classified as either definite, probable, unable to determine, or not AMI ^[29, 32]. Events will be considered "probable" if the available information from the medical record strongly suggests an AMI but some criteria required for a definite AMI are missing. Detailed adjudication criteria are provided in Appendix 1.

6.2.3 Definition of primary AMI outcome

For the primary outcome, AMI will be defined as definite plus probable Type 1 AMI ^[31, 32]. A Type 1 AMI is due to a primary coronary event, such as plaque rupture, ulceration, fissuring, erosion, or dissection with resulting intraluminal thrombus in one or more of the coronary arteries leading to decreased myocardial blood flow or distal platelet emboli with ensuing myocyte necrosis. The patient may have underlying severe coronary artery disease (CAD) but on occasion non-obstructive or no CAD.

6.3 Covariates

Patient characteristics will be identified through electronic health records. Covariates to be considered will include:

- 1. Age, sex, race / ethnicity, socioeconomic status
- 2. Duration of membership prior to index dose of hepatitis B vaccine
- 3. Diabetes status in year prior to index dose of hepatitis B vaccine
- 4. Prior AMI occurrence or coded history of AMI in year prior to index dose of hepatitis B vaccine
- 5. Other cardiovascular disease risk factors in year prior to index dose of hepatitis B vaccine (smoking, hypertension, HbA1c levels, and serum LDL-C levels)
- 6. Other co-morbidities in year prior to index dose of hepatitis B vaccine (dyslipidemia, depression, obesity, coronary artery disease including revascularization, chronic kidney disease, cancer, rheumatologic conditions, liver disease)
- 7. Other conditions included in the Charlson co-morbidity index in year prior to index dose of hepatitis B vaccine
- 8. Cardiovascular disease medications in year prior to index dose of hepatitis B vaccine (oral anticoagulants, antiplatelet agents, heparin, antihypertensive meds, statins, insulin, oral hypoglycemic agents)
- 9. Hepatitis B vaccination in year prior to index dose of hepatitis B vaccine
- 10. Healthcare utilization in year prior to index dose of hepatitis B vaccine
- 11. Concomitant receipt of other vaccines, eg, influenza or pneumococcal
- 12. Vaccinations within the 13-month follow-up period after index dose of hepatitis B vaccine

As these covariates are comprised of basic characteristics, risk factors, and important comorbidities that are usually captured during healthcare encounters, and patients have strong incentive to obtain care within KPSC, it is expected that data will be reasonably complete.

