2.0 INTRODUCTION

Hepatitis B is a viral infection causing substantial morbidity and mortality. In 2015, there were an estimated 21,900 new acute cases, and an estimated 850,000 to 2.2 million people living with chronic hepatitis B disease in the U.S., with many unaware of infection ^[1]. The risk of developing chronic disease after infection is 90% in infants, 25% to 50% in children, and 6% to 10% in adults ^[7, 8]. Asian Americans and Pacific Islanders comprise more than half of Americans living with chronic hepatitis B. Approximately 1% of acute hepatitis B infections result in liver failure and death, and of those with chronic disease, 15% to 25% are at risk of death from cirrhosis or hepatocellular carcinoma ^[9-12].

Most new infections of hepatitis B are in adults ages 30 years and older, as the younger population has been largely protected since 1991 with universal hepatitis B vaccination of infants and catch up vaccination of adolescents ^[1, 13]. Hepatitis B vaccination has been recommended since 1981 for adults at higher risk of exposure, including sexual exposure (unprotected sex with an infected partner, multiple sexual partners, men who have sex with men); percutaneous or mucosal exposure (injection drug use, chronic kidney disease, healthcare workers); travelers to countries with a high prevalence of hepatitis B; and persons with chronic liver disease, hepatitis C, or human immunodeficiency virus ^[2]. As persons with diabetes mellitus have an increased risk of exposure if diabetes-care equipment is shared, they should be vaccinated for hepatitis B if younger than 60 years of age ^[3, 4].

Approved single-antigen hepatitis B vaccines for adults include Recombivax HB (Merck) and Engerix-B (GlaxoSmithKline)^[14]. These are comprised of recombinant hepatitis B surface antigen (HBsAg) with an aluminum salt adjuvant and require 3 doses over 6 months. Coverage of hepatitis B vaccination has remained low in adults. In 2015, 24.6% of adults age 19 years or older were vaccinated with at least 3 doses. Among persons with diabetes ages 19-59 years of age, 24.4% were vaccinated with at least 3 doses ^[15, 16].

Dynavax has developed HEPLISAV-B for hepatitis B vaccination of adults. HEPLISAV-B is a hepatitis B vaccine comprised of recombinant yeast cell-derived HBsAg and a proprietary 22-mer phosphorothioate oligodeoxynucleotide adjuvant, 1018^[5]. Two doses of HEPLISAV-B are

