required, with the second dose 1 month after the first; this schedule may reduce barriers and improve vaccination coverage of adults. Furthermore, HEPLISAV-B has demonstrated significantly greater and earlier seroprotection compared to Engerix-B, including in persons with diabetes.

Safety data from adults who received at least 1 dose of HEPLISAV-B in pre-licensure clinical trials have demonstrated a similar safety profile when compared to the licensed hepatitis B vaccine, Engerix-B. Adverse events were generally mild and infrequent. The rates of serious adverse events and events leading to study discontinuations were also similar between HEPLISAV-B and Engerix-B except for a numerical imbalance in events coded with the Medical Dictionary for Regulatory Activities (MedDRA) preferred term of *acute myocardial infarction* (AMI) in a single trial, HBV-23 (HEPLISAV-B: 0.25% [n = 14]; Engerix-B: 0.04% [n = 1]). The myocardial infarctions occurred in subjects in whom such events would be expected based on their high prevalence of baseline cardiovascular risk factors, occurred randomly with no temporal relationship to time of vaccine administration, occurred at lower than expected incidence rates, and were not related to a persistent inflammatory state or an autoimmune condition ^[6]. Based on the totality of the data, the imbalance was most likely due to random variation in the small number of events reported but did not unequivocally prove no increase in risk. However, this risk of acute myocardial infarction will be monitored in the post-marketing observational surveillance study described in this protocol.

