7.3 Primary Analysis

For the final analysis of the primary objective, we will use a non-inferiority framework to test the null hypothesis of increased risk of Type 1 AMI among HEPLISAV-B recipients versus comparator vaccine recipients. Based on anticipated number of confirmed events, the study will have approximately 87% power to exclude a hazard ratio of 2.0 or greater (Section 7.9), testing the hypothesis: H_0 : $HR \ge 2$, H_a : HR < 2.

The rates of occurrence of first Type 1 AMI event during the study period among HEPLISAV-B recipients and comparator vaccine recipients will be compared using a Cox proportional hazards regression model employing inverse probability of treatment weighting (IPTW)^[33]. The IPTW provides an assessment of the closeness of match in the weighted analysis across all variables, providing a sense of the degree of control of imbalance between the vaccine exposure groups. Two tables will be created comparing the cohort of HEPLISAV-B recipients to the cohort of recipients of the comparator vaccine. The first table will be unweighted, showing the true distribution of recipient characteristics. The second table will be weighted by the inverse probability of treatment as estimated by a propensity score model. Standardized difference scores will be used to assess whether balance of covariates is achieved between the cohorts. These 2 tables will show the effectiveness of the weighting at reducing effective differences between the cohorts.

The primary analysis will be conducted on confirmed Type 1 AMIs. Variables to consider in the propensity model are listed in Section 6.3. The primary exposure will be vaccine group

(HEPLISAV-B vs. comparator vaccine), and the outcome will be confirmed AMI. Clustering by medical center will be considered through random effects variables representing medical center. Censoring events will include end of study, disenrollment from Kaiser Foundation Health Plan (allowing for a 31-day gap in membership), and death from causes other than AMI. A hazard ratio of AMI for HEPLISAV-B versus the comparator vaccine, adjusted for potential confounding factors, and associated 95% confidence interval will be reported.

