7.7 Model Selection Rationale

Potential confounders to include in multivariable models are listed in Section 6.3. These covariates will be assessed for their availability and ability for adjusting crude results, including an examination of their distributions and missingness. Bivariate associations of potential confounders with the outcome (AMI), exposure, and each other will be examined. For those with suggestions of imbalance with either exposure or outcome, the association between exposure and outcome will be stratified by categories of the potential confounder to look for differences across strata (potential effect modification) and influence on summary estimates of association (confounding). The variables will ultimately be selected based on a combination of the a priori decisions and a qualitative assessment of the empirical relationships. We will assess the robustness of cut-point selections and groupings and consider tightly confounded variables and their collinearity. Note that we will NOT use an algorithmic backward, forward or stepwise process, and that the results of the multivariable model should corroborate the knowledge gained during the model-building process.

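### Section 6.3 item 12 offers vaccinations received during follow-up as a candidate for the primary propensity model; if selected, it can bias the hazard ratio.

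*Protocol*

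**What the plan says.** Section 6.3 introduces its list with "Covariates to be considered will include". Items 2 to 10 are tied to the time before the index dose. Item 1 is demographic, and item 11 concerns other vaccines given concomitantly. Item 12 is the only one explicitly measured afterwards: "Vaccinations within the 13-month follow-up period after index dose of hepatitis B vaccine".

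The list is then used as follows:

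- Section 7.3, primary inverse-probability-weighted analysis: "Variables to consider in the propensity model are listed in Section 6.3".
- Section 7.4.1, models adjusted for or stratified by propensity score: the same candidates as the primary analysis. The traditional Cox model in that section is limited to demographics and comorbidities.
- Section 7.7: "Potential confounders to include in multivariable models are listed in Section 6.3". Variables are examined further "For those with suggestions of imbalance with either exposure or outcome", and the final choice is a matter of judgement: "The variables will ultimately be selected based on a combination of the a priori decisions and a qualitative assessment of the empirical relationships".

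Section 6.1 makes the index dose the exposure, and Section 6.2 makes the first AMI in the following 13 months the outcome. Section 2.0 says that the existing vaccines come "with an aluminum salt adjuvant and require 3 doses over 6 months", while two HEPLISAV-B doses are "required, with the second dose 1 month after the first".

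**The concern.** A propensity score models who received which vaccine at the index dose. Something that happens later cannot have influenced that assignment. Item 12 has two further problems.

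- **It is partly a result of arm.** A patient starting the series has one further HEPLISAV-B dose to receive, but two further comparator doses. If item 12 is a count of later hepatitis B doses, the group with two later doses is essentially comparator-only, and no weighting can balance it.
- **It may be partly a result of the outcome.** A patient who has an early AMI, dies or leaves the plan has less opportunity to be vaccinated again. Conditioning on the count can then group patients by whether they had the event.

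The selection process offers little protection. The Section 7.7 screen looks for imbalance with exposure or outcome. A variable that follows from both would tend to be flagged for adjustment. The propensity-score sensitivity models share the candidate, so they could repeat the error. At stake is the study's main claim, the exclusion of an HR of 2.0 or more.

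**Working it through.** **1. The plan's own figures.** Power = Φ(ln 2 × √d / 2 − 1.960), with d events, 1:1 allocation and one-sided alpha 0.025 (Section 7.9, Table 7-1).

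- d = 78: 0.6931 × 8.832 / 2 − 1.960 = 1.101, so power is 0.8645 (stated 0.865).
- d = 41 gives 0.602 (stated 0.603); d = 68 gives 0.815 (stated 0.814).

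With 78 events the standard error of ln HR is 2/√78 = 0.2265. The largest estimate that still excludes 2.0 is exp(0.6931 − 1.960 × 0.2265) = 1.283.

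**2. Illustration with a dose count.** The protocol gives no uptake by dose and no coding for item 12, so these are assumptions:

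- true HR 1 and no confounding;
- item 12 is the number of later hepatitis B doses;
- dose 2 at month 1 in both arms, comparator dose 3 at month 6;
- AMI uniform over 13 months, with no doses after an AMI;
- uptake 60% (HEPLISAV-B dose 2), 60% (comparator dose 2), 30% (comparator dose 3). Section 5.2 puts three-dose coverage in adults with diabetes below 30%.

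AMI is rare (78 in about 50,000), so the propensity score is taken from patients without an event. Among patients with an event, dose 2 is counted in 0.60 × 12/13 = 0.554 and comparator dose 3 in 0.30 × 7/13 = 0.162.

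| Later doses | HEPLISAV-B share | Comparator share | Propensity | HEPLISAV-B weight | Comparator weight | HEPLISAV-B share of AMI | Comparator share of AMI |
|---|---|---|---|---|---|---|---|
| 0 | 0.40 | 0.40 | 0.500 | 2.0 | 2.0 | 0.446 | 0.446 |
| 1 | 0.60 | 0.30 | 0.667 | 1.5 | 3.0 | 0.554 | 0.392 |
| 2 | 0 | 0.30 | 0 | – | 1.0 | 0 | 0.162 |

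Weighted relative rate = (weighted AMI share) / (weighted patient share):

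- HEPLISAV-B: (0.446 × 2 + 0.554 × 1.5) / (0.40 × 2 + 0.60 × 1.5) = 1.723 / 1.70 = 1.014.
- Comparator: (0.446 × 2 + 0.392 × 3 + 0.162 × 1) / (0.40 × 2 + 0.30 × 3 + 0.30 × 1) = 2.231 / 2.00 = 1.115.
- Ratio: 1.014 / 1.115 = 0.909.

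If the same factor applies at a true HR of 2.0, the chance of wrongly excluding 2.0 is Φ((ln 1.283 − ln(2 × 0.909)) / 0.2265) = Φ(−1.537) = 6.2%, against 2.5% without the bias. This ignores variance inflation from the weights.

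**3. Varying the uptakes.** Over 50–80%, 50–70% and 20–30%, the same formula gives ratios from 0.88 (for example 60/50/30) to 0.996 (80/55/20). On a grid in steps of 10 points for dose 2 and 5 points for dose 3, the median is 0.93. So 0.91 is one case within the range, not its centre.

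**4. Varying how often an AMI stops later doses (60/60/30%).**

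| AMI stops later doses in | Weighted HR | Chance of wrongly excluding 2.0 |
|---|---|---|
| all cases | 0.91 | 6.2% |
| half | 0.95 | 4.1% |
| a quarter | 0.975 | 3.2% |
| none | 1.00 | 2.5% |

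**5. Varying the coding.** With a yes/no indicator for any later dose, always stopped by AMI, the formula gives 1.00 at equal uptake. It gives 1.02 at 70% v 60% (HEPLISAV-B first), 1.03 at 60% v 40%, and 0.98 at 50% v 60%.

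**6. Cross-check by simulation** (6 million per arm, 1.5 per 1,000 person-years, 13 months, 10% uniform loss). The 60/60/30% count gives about 0.92 and an error of about 6%. The yes/no indicator moves in the same directions but further: 1.05, 1.07 and 0.97 for the three unequal cases above. Receipt of other vaccines gives 1.00 at equal uptake and 1.11 at 60% v 50%. If an AMI does not stop later doses, weighting gives about 1.00 in every scenario.

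**The case against.** The case on the other side has real weight.

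- **The list is of candidates.** Section 6.3 speaks of covariates to be considered, and Section 7.7 leaves the choice to judgement and rules out algorithmic selection. A reader might infer that the primary HR is biased as planned. The protocol does not commit to using item 12, so that inference fails; any bias is conditional on its selection.
- **Item 12 says vaccinations in general.** It follows an item on influenza and pneumococcal vaccines, while item 9 names hepatitis B explicitly. Dependence on arm through the schedules, and the comparator-only group, apply to hepatitis B doses. For other vaccines a bias needs uptake that differs by arm. Patients whose index dose is already a second or later dose (Section 6.1) also have fewer doses left.
- **Direction.** A reader might infer that the bias favours HEPLISAV-B. That holds for a dose count. A yes/no indicator, or other vaccines, can move the HR upward, which is conservative for this test.
- **AMI stopping later doses is an assumption.** Under Section 4.4 follow-up ends at disenrollment, death or 13 months, not at AMI, so a survivor's later doses could still count.
- **Immortal-time bias is not the right label.** Both arms start at the index dose and nobody must survive to be classified. The fault is conditioning on a post-exposure variable.
- **Partial safeguards exist.** The traditional Cox sensitivity model leaves item 12 out, standardized differences would show a group that cannot be balanced, and Section 7.4.2 lets the data monitoring committee (DMC) suggest further analyses if results disagree.

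All of this limits the size and certainty of the harm. None of it makes a follow-up variable a valid baseline covariate, and no section sets it aside. The safeguards would act only after the primary estimate had been produced.

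**Conclusion.** The point stands in conditional form. The protocol offers a post-exposure variable as a candidate for the primary propensity model, and its screening rule would tend to flag that variable rather than remove it. This is a matter of what the text says, not of detail left to an analysis plan.

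If item 12 is selected, the primary HR can be biased by an amount and in a direction that the documents do not fix. The range of 0.88 to 0.996, and the 6% error in the 60/60/30% case, are illustrations. They rest on assumed uptakes, a hepatitis B dose count, AMI always ending later doses, and no variance inflation from weighting. Other codings can push the HR above its true value, and with no effect of AMI on later doses the bias disappears. The candidate has no role in controlling confounding at the index dose, so there is no gain to set against this risk.

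**What to change.** Take item 12 out of the adjustment candidates in Section 6.3. Make Sections 7.3, 7.4.1 and 7.7 state that every propensity or adjustment covariate is measured on or before the index date. That statement would also settle the timing of item 11.

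Later vaccinations can stay in the descriptive tables of Section 7.2. If their effect is of interest, analyse them as a time-varying exposure in an exploratory analysis under Section 7.6. Make the change before outcomes are compared by arm.

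The cost is a line or two of text. No extra data are needed, and the planned 78 events and power of about 87% are unchanged.

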6.4 Data Sources and Claims

The study will be conducted using the KPSC Research Data Warehouse (RDW) which supports external and internal research projects conducted in the KPSC Department of Research and Evaluation as well as patient care management programs. The data warehouse is an integrated

and comprehensive resource of electronic health records. It contains information as far back as 1980, including records related to membership, benefits, utilization, pharmacy, vital signs, laboratory, vaccines, geocoding, mortality, and procedures. Data are linked through a unique medical record number assigned to each member of the health plan.

Care received outside of KPSC, including emergency care for patients experiencing AMI, is integrated into the RDW. If a patient is transferred to KPSC, then records for care at the outside facility, such as ECG strips and biomarker levels, are usually transferred and incorporated into the patient's health records. Patients who are not transferred often have documentation incorporated as part of the claims process or through Care Everywhere. Patients with potential AMI diagnoses who are missing records will be contacted and asked for permission to retrieve their medical records from non-KPSC facilities.

Because claims can take several months to be incorporated into electronic health records, a 3-month lag period will be used to allow for data settling. Thus, data will be reported through the date 3 months prior to the date of the data pull for the report (Section 6.5). The 3-month lag is essential to avoid bias in the number of AMI events, as there may be differences between target and comparator medical centers in the proportion of events derived from claims.

6.5 Data Monitoring

An independent Data Monitoring Committee (DMC) will be established, comprised of a cardiovascular disease epidemiologist, a biostatistician familiar with vaccine post-licensure safety studies, and a vaccine safety expert. The committee members will be proposed and retained by KPSC. The DMC will review quarterly reports of vaccine accrual and aggregated number of unconfirmed AMI cases, and the interim and final analyses, as specified below.

The number of patients receiving any dose of hepatitis B vaccine and the aggregate number of unconfirmed AMIs will be compiled monthly to monitor assumptions used to determine study duration (vaccine uptake and AMI event rates). The number of vaccines will be identified by cluster and age strata (<50 years and \geq 50 years) and will be available beginning 3 months after the first HEPLISAV-B dose is administered. The number of AMI events will be aggregated across all medical centers and not by vaccine group, to avoid 'spending' type 1 error. As noted above, a 3-month lag period will be used to allow incorporation of claims data (Section 6.4), so the number of AMI events will first be available beginning 4 months after the first HEPLISAV-B dose (1 month of patient follow-up plus 3 months for data settling). After this 4-month period, KPSC will provide the reports to the sponsor monthly and to the DMC quarterly. These data will be used to monitor uptake and event rates that can be compared to the assumptions in the sample size calculation and help anticipate the need for extension of the study, if necessary. If HEPLISAV-B accrual is slower than anticipated or if observed AMI event rates are lower than

anticipated, the number of patients receiving HEPLISAV-B could be increased, along with an equivalent number of patients receiving comparator vaccine, by extending the study vaccination period.

